7.8. Definition of End of Study

The end of the study is following the final interview of the last patient (which could be on the ward or by telephone).

8. INTERVENTIONS

8.1. Interventions during anaesthesia

Nothing listed below deviates from normal clinical practice for any similar SAD device, or for almost any type of anaesthetic:

Preoperative assessment:

During the preoperative visit, patient information leaflet will be given to the patients meeting the eligibility criteria.

Wherever possible, suitable patients will be identified in the preoperative assessment clinic and the information leaflet given. They will be given adequate time to read this information and any queries will be answered before being asked to sign a consent form. A detailed airway assessment will be performed by one of the investigators and documented on the study proforma.

Induction of anaesthesia:

On arrival in the anaesthetic room patients will be monitored with pulse oximetry, electrocardiography and invasive or non-invasive blood pressure measurements. After intravenous access is secured and the pre-surgical checklist completed, all patients will be pre-oxygenated using a facemask to achieve end tidal oxygen concentration of at least 80%. A 'sniffing' position of the head and neck and a 20 degree head-up bed tilt will be used for pre-oxygenation. General anaesthesia will be induced intravenously. After induction of anaesthesia, facemask ventilation will be commenced and anaesthesia maintained with an inhalational anaesthetic agent in oxygen or with total intravenous anaesthesia. The volatile agent's (anesthetic gases) concentration of 1 MAC adjusted for the patient's age will be achieved and maintained. This is normal process of anaesthesia applicable for all patients irrespective of participation in the study.

Supraglottic airway device (SAD) insertion:

Once deep plane of anaesthesia is confirmed, with the absence of movement to jaw thrust stimulation the SAD (LMA protector) will be inserted. The size of the device will be based on the manufacturer's recommendations for the body weight. The breathing system will be connected to the device. Ventilation of the lungs will be then confirmed by observing adequate bilateral chest inflation and square end-tidal capnogram wave with positive pressure ventilation. Adequate ventilation will be recorded if three tests are passed: 1) adequate chest movement, 2) an expired tidal volume of at least 7 ml/kg and 3) stable oxygenation. Time would continue until LMA® ProtectorTM inserted successfully. If it is not possible to insert the device or ventilate through it, two more attempts at placement of the device will be allowed. If placement has failed after two further attempts, the study will be abandoned and the other device will be used. If this fails on first attempt a different LMA or tracheal tube will be used as appropriate.

Maintenance of anaesthesia and recovery

At the end of operation, anaesthetic agents will be discontinued while the device is left in place. The device will be removed after the patient has regained consciousness, and has responded to verbal command to open the mouth. Any complications that occur during the use of the device will be recorded.

Postoperative assessment

Postoperatively in recovery or on the ward, we will visit each patient and determine whether the following airway complications are present after surgery: sore throat (constant pain, independent of swallowing), dysphagia (difficulty in, or pain provoked by, swallowing), sore jaw, dysphonia (difficulty in, or pain on, speaking), numbness of the tongue or the oropharynx, ear pain, neck or mouth ache, hearing changes. Each complication will be graded as none, mild, moderate or severe. The same questions will be asked 24-48 hours later.

The main interventions refer to the insertion of the airway device into the patient to obtain a airway and allow the conduct of the anaesthetic and therefore the surgery. However, if there are problems with the device and the airway obtained is suboptimal then the below interventions are allowed (which will be noted in the data collection form):

- 1) Neck extension – move patient's neck upward
- 2) Neck flexion – move patient's neck downward
- 3) Chin lift - manoeuvre to open the airway
- 4) Jaw thrust – manoeuvre to open the airway
- 5) Reposition of the device

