5. STUDY DESIGN

This is a prospective, multi-centred cohort observational study, where all suitable participants will have the LMA Protector used. The centres involved will be: Oxford University Hospitals NHS Foundation Trust, Northampton General Hospital, Royal Berkshire Hospital, Royal United Hospital, and University Hospital of Wales. The participants will be involved in the study for maximum 48 hours starting from approach for consent on the morning of surgery, while they are in the pre-operative area, until the second interview (either in person if participant is an inpatient, or via telephone if participant had been discharged). Data will be collected while the anaesthetic is being conducted apart from the information regarding the complications of the device removal and postoperatively. The order of events will be: a) consent, b) general anaesthetic as per standard care but using LMA protector, c) brief interview by clinician following operation in hospital at first available opportunity, d) another interview 24 to 48 hours later with the same questions either in hospital or at home by telephone.

Data that will be collected will be: a) investigator name, b) number of previous insertions of the device by the investigator, c) patient age, d) patient gender, e) weight, f) height, g) ASA class, h) operation, i) anaesthetic drugs and dosages, j) anaesthetic technique, k) mode of ventilation, l) if further muscle relaxant used. Moreover, we will collect:

- 1) Airway assessment including Malampatti classification
- 2) The number of attempts at the insertion will be recorded

- 3) Volume of air in cuff to achieve intracuff pressure of 60cmH₂O
- 4) Airway leak pressure
- 5) The ease of insertion
- 6) The lowest oxygen saturation recording
- 7) The quality of ventilation
- 8) The quality of the airway during maintenance
- 9) The ease of hands free anaesthesia
- 10) The overall usefulness of the device in the patient
- 11) The overall performance of the device
- 12) The time to first square capnography trace
- 13) Positive or negative bubble test
- 14) Airway manipulations to establish airway
- 15) Complications on insertion, during use, and on removal of the device
- 16) Post-operative oropharyngeal sequelae

The data will be collected from the anaesthetic record. Data c, d, e, f will be collected from the electronic notes.

All data will be recorded in the CRF/data collection form.

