7.4. Randomisation, blinding and code-breaking

Participants will not be randomised in this study. We are evaluating the performance of the LMA Protector airway device and thus if the participant signs the consent form the device will be used for their anaesthetic.

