7.7. Discontinuation/Withdrawal of Participants from Study

Each participant has the right to withdraw from the study at any time. In addition, the Investigator may discontinue a participant from the study at any time if the Investigator considers it necessary for any reason including:

- Ineligibility (either arising during the study or retrospectively having been overlooked at screening)
- Significant protocol deviation
- Significant non-compliance with treatment regimen or study requirements
- Withdrawal of Consent
- Loss to follow up

The reason for withdrawal will be recorded in the CRF.

If the device cannot be inserted after 3 unsuccessful attempts to insert it, the study will be stopped, an alternative airway device will be used and the failure noted on the CRF. Participants who have been withdrawn will not be replaced. If a patient is withdrawn their research data will not be used in final analysis.

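### The attempt limit has different triggers in 7.7 and 8.1, and a bare attempt count cannot separate first-go insertion failure from first-go ventilation failure

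*Combined protocol and SAP*

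**What the plan says.** **Section 8.1 (device insertion).** The retry rule is: "If it is not possible to insert the device or ventilate through it, two more attempts at placement of the device will be allowed". The stopping sentence follows: "If placement has failed after two further attempts, the study will be abandoned and the other device will be used". Then comes a second step: "If this fails on first attempt a different LMA or tracheal tube will be used as appropriate".

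**Section 7.7 (discontinuation and withdrawal).** "If the device cannot be inserted after 3 unsuccessful attempts to insert it, the study will be stopped", and then "an alternative airway device will be used and the failure noted on the CRF".

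**One device only.** Section 5 describes a cohort "where all suitable participants will have the LMA Protector used". Section 7.4 says that "if the participant signs the consent form the device will be used for their anaesthetic". Section 10.1 calls the study single arm. No second study device is named anywhere.

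**Outcomes and data.** Section 4 lists first-go insertion success and first-go successful ventilation as separate primary outcomes. Sections 5 and 7.5 and Appendix A list insertion attempts as a count. Section 8.1 sets three tests for adequate ventilation. Appendix A adds a 0 to 10 score for adequacy of ventilation, and a complication list that includes failing to establish an airway. None of these items is tied to a particular attempt.

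**The concern.** The two sections describe the same event, the end of study use of the device in a patient, but do not define it in the same way. A device that is inserted three times and never ventilates uses up its attempts under 8.1, yet lies outside 7.7 as worded. Section 7.7 is also the rule that carries the explicit failure note. The fallback wording differs too, and the version in 8.1 points to a device that the study does not have.

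The statistical stake lies at the first attempt. Under 8.1 an attempt can be spent on either kind of failure. If only the count is kept, two primary outcomes that are meant to be different rates cannot be told apart in exactly the patients where they could differ.

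**Working it through.** **Step 1. The two rules side by side.**

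| | Section 7.7 | Section 8.1 |
|---|---|---|
| Attempts allowed | 3 | 1 + 2 = 3 |
| What uses up an attempt | Failure to insert | Failure to insert, or failure to ventilate |
| What ends study use | Not insertable after 3 attempts | Placement failed after the two further attempts |
| First fallback | Any alternative airway device | A specific second device, not identified |
| Further fallback | None stated | Another laryngeal mask or a tracheal tube |
| Failure note on CRF in the rule | Yes | No |

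The attempt limit is the only figure that the plan gives here, and it agrees. The trigger and the fallback do not.

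**Step 2. The fallback in 8.1.** Sections 5, 7.4 and 10.1 leave one device and one arm, so the definite reference in 8.1 has nothing to attach to. It cannot mean the further fallback either, because that is used only if the first one fails.

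**Step 3. What a count can show.** A first attempt can end in three ways. The table takes insertion success as distinct from ventilation success, as the separate outcomes in section 4 imply.

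| First attempt | First-go insertion | First-go ventilation | Count under 8.1 |
|---|---|---|---|
| Not inserted | Fail | Fail | 2 or more |
| Inserted, not ventilating | Success | Fail | 2 or more |
| Ventilating | Success | Success | 1 |

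The count separates the third row from the first two, so first-go ventilation can be derived. It does not separate the first row from the second, so first-go insertion cannot be derived for anyone with two or more attempts.

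**Step 4. Size.** The documents give no rates, so these are assumptions. Let p be the share of patients who need a second attempt, and q the share of those first attempts that were inserted but did not ventilate.

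- Insertion success read from the count: 1 − p
- Insertion success counting insertion failures only: 1 − p(1 − q)
- Difference: pq

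With p = 8%, q = 50% and the 1100 patients of section 10.2:

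- Second attempts: 0.08 × 1100 = 88
- Of these, inserted but not ventilating: 0.5 × 88 = 44
- By count: 1 − 88/1100 = 92%
- By insertion failures only: 1 − 44/1100 = 96%

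Range for the unknown q, with p held at 8%: q = 0 gives 1 − 0.08 = 92%, with no difference; q = 1 gives 1 − 0 = 100%, a difference of 8 percentage points. In general the difference runs from 0 to p.

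**The case against.** Several points on the other side are sound.

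- **The gap inside 8.1.** A reader might infer that a seated, non-ventilating device also escapes the stopping sentence in 8.1, because that sentence speaks only of placement. But it directly continues a sentence on placement attempts that are triggered by either failure, so the natural reading carries the ventilation trigger over. Only 7.7 is clearly narrower.
- **Logging.** A reader might infer that a device that never ventilates is nowhere to be logged as a failure. Appendix A contradicts that: its complication item for failing to establish an airway covers such a case, and adequacy of ventilation is recorded separately. What remains is that these entries identify neither the attempt nor the type of failure.
- **Patient safety.** A reader might infer that the operator is left without a way forward. The documents do not support this. Both sections allow three attempts and both give a route onward, and section 3 requires investigators to have used similar devices more than 200 times. The fallback wording is inconsistent, but nothing shows that it would misdirect care.
- **The illustration.** The stopping rule acts after the third attempt, whereas both first-go outcomes are settled at the first. Reconciling 7.7 with 8.1 would therefore not move any of the 44 patients. The 92% and 96% measure the missing first-attempt record, not the conflict between the stopping rules.
- **The form.** The CRF is not among the documents and may ask for more. The point is limited to what the protocol requires to be recorded.

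**Conclusion.** Two linked defects stand. First, 7.7 and 8.1 agree on three attempts but conflict on the trigger and on the fallback, and the fallback in 8.1 has no referent in a single-device study. Second, the protocol requires only a count of attempts, so the first primary outcome cannot be separated from the second in patients with two or more attempts. Unless the form asks for more than the protocol lists, this cannot be recovered later.

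The size is the product pq: 4 percentage points at the assumed p = 8% and q = 50%, and anything from 0 to 8 points as q varies. This rests on insertion success not itself requiring ventilation. The plan does not define it, but listing two separate outcomes implies it.

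A reader might go further and infer that the choice of trigger decides the device failure rate at the interim analysis. The documents do not support that step: section 10.3 does not define the failure rate or link it to either stopping rule. The defects are worth correcting but do not undermine the design.

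**What to change.** 1. Reconcile 7.7 and 8.1 so that one trigger governs both the attempt limit and the failure note on the CRF. The clinical rule is the sponsor's choice.
2. Replace the undefined fallback device in 8.1 with wording that has meaning in a single-arm study and agrees with 7.7.
3. Record one outcome for each attempt: not inserted, inserted but not ventilating, or ventilating.
4. State that first-go insertion success and first-go successful ventilation are both derived from the attempt 1 entry.

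The cost is a wording amendment to two sections, a line on derivation, and one three-option tick box per attempt. No study procedure is added.

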4. OBJECTIVES AND OUTCOME MEASURES

Objectives	Outcome Measures	Timepoint(s) of evaluation of this outcome

		measure (if applicable)
Primary Objective To assess the performance of the LMA Protector	1) First go insertion success rate, 2) First go successful ventilation rate, 3) Percentage of complication free insertions	At time of anaesthesia
Secondary Objectives To assess: 1) Time taken to achieve airway 2) Number of attempts to achieve patent airway 3) Complications during airway insertion 4) Complications during anaesthesia attributed to the airway 5) Complications during device removal 6) Complications after anaesthesia attributed to the airway 7) Quality of ventilation	1) Time to first square capnography waveform 2) Lowest oxygen saturation level 3) Monitor numbers of interventions needed to ensure airway patency 4) Monitor pre-defined complications occurrence during insertion of device, during anaesthesia, and on device removal 5) The quality of ventilation will depend on whether there was: a) adequate chest movement, b) tidal volume $> 7\text{ml/kg}$, c) stable SpO ₂ , and d) square capnography trace	At time of anaesthesia and post-operatively

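### Sections 7.7 and 8.1 end the study for a patient at failed placement, yet 8.1 plans to visit every patient, so follow-up of device failures is unclear and post-operative complication rates may be biased low

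*Combined protocol and SAP*

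**What the plan says.** **Stop rule.** Section 7.7, under discontinuation and withdrawal, covers three unsuccessful attempts: "the study will be stopped, an alternative airway device will be used and the failure noted on the CRF". It then says that withdrawn participants are not replaced and that "If a patient is withdrawn their research data will not be used in final analysis". Section 8.1 describes the same situation (a first attempt plus two more): "If placement has failed after two further attempts, the study will be abandoned and the other device will be used".

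**Follow-up.** The post-operative part of section 8.1 makes no exception for failed placement: "Postoperatively in recovery or on the ward, we will visit each patient and determine whether the following airway complications are present after surgery". It adds: "The same questions will be asked 24-48 hours later". Section 7.6 lists ten graded symptoms for each of the two contacts. Section 5 defines participation as running from the approach for consent to the second interview.

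**Recording during anaesthesia.** Section 7.5 lists number of attempts, lowest saturation, airway manipulations, and complications at insertion, during the operation, at removal and afterwards. Appendix A includes failure to establish an airway and desaturation among the complications to note. Section 8.1 says "Any complications that occur during the use of the device will be recorded".

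**Outcomes affected.** Section 4 has "Complications after anaesthesia attributed to the airway" as a secondary objective and lowest oxygen saturation as a secondary outcome measure.

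**The concern.** Two different events are run together: ending attempts with the study device, and ending the patient's participation. A site that takes the stop rule at its word closes the form when placement fails. A site that follows the post-operative paragraph carries on and interviews the patient twice. Both can claim to be following the protocol.

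Any resulting loss would depend on outcome, because it falls only on patients in whom the device failed. Post-operative complication rates would then describe patients with successful placement but be presented as rates for the cohort. If failures have more sequelae than successes, the reported rates are too low.

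The problem could also go unnoticed. Under section 11.2 each site manages its own data and sends it to the lead team only when collection has ended. An analysis rule can be changed at that stage, but a 24-48 hour interview that was never held cannot be recovered.

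**Working it through.** **1. The plan's own figures.** Section 10.3 gives upper 95% limits of 6.54% (n = 1000) and 6.05% (n = 2000) at a 5% failure rate. Exact (Clopper-Pearson) limits for 50/1000 and 100/2000 are 6.539% and 6.048%, so both reproduce. They are not in dispute. Section 10.3 does not say that its 5% means final failure of placement, so the share of patients affected has to be assumed.

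**2. What is exposed after failed placement.**

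| Data | Position in the documents |
|---|---|
| Attempts, saturation and complications up to failure | To be recorded (sections 5 and 7.5, Appendix A) |
| Saturation and complications under the replacement airway | Unclear. Section 8.1 ties recording to use of the device; section 5 names the anaesthetic record as a source, so recovery may be possible |
| First interview and 24-48 hour interview | Contradictory: ended by the stop rule if participation ends, but planned for every patient in 8.1 |
| Identity of the replacement airway | Not named among the items in sections 5 and 7.5 or Appendix A; the CRF itself is not in the documents |

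**3. Number of patients.** Patients affected = N × f, where f is the assumed share with final failure. For f = 2%, 3% and 5% this is 22, 33 and 55 of 1100, or 40, 60 and 100 of 2000.

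**4. Possible bias in an interview outcome.** Let p_S and p_F be the complication rates in successes and failures.

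- True rate = (1 − f) × p_S + f × p_F
- Reported rate without the failures = p_S
- Understatement = f × (p_F − p_S)

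Assume sore throat at p_S = 20% and p_F = 50%; neither value is in the documents:

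- f = 2%: 0.98 × 20% + 0.02 × 50% = 20.6%, understated by 0.6 points
- f = 3%: 0.97 × 20% + 0.03 × 50% = 20.9%, understated by 0.9 points
- f = 5%: 0.95 × 20% + 0.05 × 50% = 21.5%, understated by 1.5 points

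If p_F = p_S, the understatement is zero.

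**5. Wider range.** With p_S = 10%, p_F = 30% to 50% and f = 1% to 10%, the understatement runs from 0.01 × 20 = 0.2 points to 0.10 × 40 = 4.0 points.

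**6. Against sampling error.** At 20% the approximate 95% half-width is 1.96 × √(0.2 × 0.8 / n): 2.4 points at n = 1100 and 1.8 points at n = 2000. The 0.6-1.5 point bias is smaller than either, but unlike sampling error it does not shrink as n grows.

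**The case against.** The strongest reply is that nothing in the documents says the data are lost. Abandoning the study can mean only that use of the study device ends, and the promise to visit each patient can be read to include failures. That stands: loss is an inference from one reading.

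Three other stronger readings are tempting, and the documents do not support them.

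- **That the failure itself is the only thing recorded.** Sections 5 and 7.5 and Appendix A require attempts, saturation and insertion complications without exempting failures.
- **That everything after failure is irrecoverable.** Intra-operative data may be available from the anaesthetic record. Section 9.2 requires follow-up to resolution of adverse device effects that lead to withdrawal, and section 9.3 requires prompt reporting of serious events.
- **That uncommon serious harms are distorted most.** Assuming harm in 1% of successes and 30% of failures, with 2-5% failed placements, gives a true rate of 1.58-2.45% against 1.0% reported. That supposes that no soft tissue damage or desaturation in failures is captured, although harm arising during the attempts is already to be recorded. It is also plausible that patients with three attempts have the most airway trauma, but no figure in the documents shows it.

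These replies narrow the point without removing it. General adverse event recording in section 9.2 applies during the study, so it gives little protection if the study has been abandoned for that patient. Following up an effect already identified does not replace asking ten graded questions twice. No safeguard clearly covers the interviews or the time under the replacement airway.

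**Conclusion.** The point holds as an unresolved contradiction with a possible outcome-dependent loss of data; actual loss is not shown. The exposure is mainly the two post-operative interviews and the period after the switch of airway. On the assumed sore throat rates and 2-5% failed placements, the overall rate would be understated by 0.6-1.5 percentage points. The true size is unknown, because the documents give neither the share of final failures nor complication rates by success and failure. The downward direction also rests on failures having the higher rate.

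A reader might go further and infer that section 7.7 already removes device failures from the analysis. The text does not say that a failed placement counts as withdrawal. The exclusion of withdrawn patients' data is a related but separate matter, and it needs one clarifying sentence here.

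The wording should be corrected because the repair is cheap and interviews that were not held cannot be added afterwards.

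**What to change.** In sections 7.7 and 8.1, replace the statements that the study stops or is abandoned with wording to this effect:

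- Failed placement ends use of the LMA Protector but is not withdrawal from the study.
- Lowest saturation, the Appendix A complications and both interviews are completed for these patients.
- The replacement airway is recorded on the CRF.
- The exclusion of withdrawn patients' data in section 7.7 does not apply to them.

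In section 10.3, state that post-operative complications are reported for all patients with an attempted insertion, noting those who were switched. Symptoms after a switch cannot be attributed cleanly to one device, so identifying these patients helps the reader.

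The sponsor must also reconcile the two accounts of what follows a failed placement. Section 8.1 refers to the other device, which has no defined meaning in a single-arm study, while section 7.7 refers to an alternative one. No clinical sequence is proposed here.

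The cost is a wording change in three sections, one CRF field if it is not already there, and interviews that 8.1 already plans. At 2-5% failed placements and two interviews each, that is 44 to 110 interviews for 1100 patients, or 80 to 200 for 2000.

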6. PARTICIPANT IDENTIFICATION

6.1. Study Participants

Inclusion Criteria

- Adult participants who are having a general anaesthetic.
- Participant is willing and able to give informed consent for participation in the study.
- Male or Female, aged 18 years or above.
- ASA 1 – 3 category patients
- Elective operations
- Urgent operations
- Patients suitable for an SAD based on patient and operation factors.

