6.2. Exclusion Criteria

The participant may not enter the study if ANY of the following apply:

- Refusal of consent
- Age less than 18 years
- Require intubation for the operation
- Risk of regurgitation
- ASA 4 and above
- Mouth opening less than 2.5cm
- Require awake intubation

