7.6. Subsequent Visits

First visit

During the first visit by the anaesthetist to the participant, at the anaesthetist's earliest opportunity, either in the recovery area or on the ward, the participants will be asked about the following complications, which will be graded as none, mild, moderate or severe).

- 1) Vomiting
- 2) Lip or tongue swelling
- 3) Hearing changes
- 4) Ear pain
- 5) Sore throat
- 6) Pain on swallowing
- 7) Jaw pain
- 8) Neck or mouth ache
- 9) Pain on speaking
- 10) Numbness of the tongue

Second visit (or telephone consultation)

During the second visit 24-48 hours post-operatively on the ward or via telephone the participants will be asked about the following complications, which will be graded as none, mild, moderate or severe).

- 1) Vomiting
- 2) Lip or tongue swelling
- 3) Hearing changes
- 4) Ear pain
- 5) Sore throat
- 6) Pain on swallowing
- 7) Jaw pain
- 8) Neck or mouth ache
- 9) Pain on speaking
- 10) Numbness of the tongue

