10. STATISTICS AND ANALYSIS

10.1. Description of Statistical Methods

The data in this single arm study will be described by descriptive statistics only, using binomial confidence where necessary.

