17. APPENDIX A: STUDY FLOW CHART

SCHEDULE OF OBSERVATIONS

SAD insertion time (from picking up device until upstroke of 1 st square wave capnography trace)
SAD insertion attempts
Cuff volume to achieve 60cmH₂O cuff pressure
Leak pressure: pressure at which audible leak starts or airway pressure plateaus, with fresh gas flow set at 5L/ min
Score following parameters using 11-point NRS (0 – very difficult / inadequate, 10 – very easy / excellent) Ease of insertion Adequacy of ventilation Hands free anaesthesia or overall usefulness of device
Note airway manipulations to maintain airway: Additional Neck extension Neck flexion Chin lift Additional Jaw thrust
Note following complications during device insertion / airway maintenance / removal of device: Failure to establish airway Loss of adequate airway Soft tissue damage Dental damage Regurgitation Aspiration Laryngospasm Stridor Coughing Gagging Hiccough Desaturation
After surgery note following events: Vomiting Lip or tongue swelling Hearing changes Ear pain Sore throat Dysphagia Sore jaw Dysphonia Numbness of tongue / oropharynx Pain on speaking Neck or mouth ache

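### Post-operative mouth, throat, jaw, ear and neck symptoms have no working link to the airway device, so operations on the same areas can bias these secondary rates upward

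*Combined protocol and SAP*

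**What the plan says.** The aim is stated in section 4. Secondary objective 6 covers complications after anaesthesia, limited to those attributed to the airway.

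Collection is described in three places:

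- Section 8.1 (postoperative assessment): "we will visit each patient and determine whether the following airway complications are present after surgery". The list runs from sore throat and dysphagia to ear pain, neck or mouth ache and hearing changes. The scale is severity: "Each complication will be graded as none, mild, moderate or severe".
- Section 7.6, at both interviews: "the participants will be asked about the following complications, which will be graded as none, mild, moderate or severe". This list adds vomiting and "2) Lip or tongue swelling", which are not in the section 8.1 list.
- Appendix A: "After surgery note following events", followed by a similar list.

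Eligibility depends on the operation in two ways only. Section 6.1 admits "Patients suitable for an SAD based on patient and operation factors", and section 6.2 excludes patients who "Require intubation for the operation". Neither names a surgical site.

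The operation is recorded (section 5, item h). Section 10.1 gives the analysis: "The data in this single arm study will be described by descriptive statistics only, using binomial confidence where necessary". Section 10.3 repeats this.

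Section 9.2 separately requires a judgement of relatedness to the device for adverse events. Section 9.1.2 treats an event as a device effect when a causal link is a reasonable possibility that cannot be ruled out.

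**The concern.** The objective asks for symptoms that come from the airway. The collection forms capture symptoms that are present, whatever their cause. For most operations the difference may be small. For operations on the mouth, jaw, ear, nose, throat or neck, the surgery itself can produce the symptoms on the list.

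A comparator arm with a similar mix of operations would carry the same surgical symptoms and so show how much they contribute. This study has none. A rate taken over all patients would then depend partly on how many such operations the five centres enrol. A sample of 1100 to 2000 would narrow the interval around that mixed quantity without bringing it closer to the device effect.

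This matters because the study is meant to establish the device's safety and its likely place in UK practice, and section 3 names post-operative sore throat among the recognised complications of supraglottic devices.

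**Working it through.** **1. The plan's own precision figures.** Section 10.3 gives upper 95% limits of 6.54% (1000 patients) and 6.05% (2000 patients) at a 5% failure rate. Exact (Clopper-Pearson) limits for 50/1000 and 100/2000 are 6.54% and 6.05%, so both reproduce. They concern device failure, not post-operative symptoms. The same interval method is used below.

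**2. Is there any step from symptom to cause?**

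| Place | What is recorded | Cause recorded? |
|---|---|---|
| Section 7.6, both interviews | ten symptoms, by severity | no |
| Section 8.1 | symptoms present after surgery, by severity | no |
| Appendix A | events noted | no |
| Section 9.2 | adverse events with relatedness to device | yes, but not linked to objective 6 |
| Section 10 | descriptive statistics, binomial intervals | no rule, no split by operation |

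No pre-operative check of the same symptoms is described either.

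**3. Size of the possible bias.** The documents give neither the case mix nor any symptom rates, so every input here except n is an assumption. Take one symptom at a time, because the plan grades each symptom separately and defines no combined endpoint. Let

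- b = rate of the symptom from all causes other than surgery on these areas,
- s = share of patients having such an operation,
- q = probability that the operation itself causes the symptom, independently of other causes.

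Observed rate = b + s × q × (1 − b).

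Example: b = 5%, s = 5%, q = 0.5 gives 0.05 + 0.05 × 0.5 × 0.95 = 0.0738, or 7.4%.

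Results at n = 1100, with exact 95% intervals on the nearest whole count:

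| b | s | q = 0.1 | q = 0.5 | q = 0.8 |
|---|---|---|---|---|
| 5% | 0 | 5.0% (3.8 to 6.5) | same | same |
| 5% | 2% | 5.2% (3.9 to 6.7) | 6.0% (4.6 to 7.5) | 6.5% (5.2 to 8.2) |
| 5% | 5% | 5.5% (4.2 to 7.0) | 7.4% (5.9 to 9.1) | 8.8% (7.2 to 10.7) |
| 5% | 10% | 6.0% (4.6 to 7.5) | 9.8% (8.0 to 11.6) | 12.6% (10.7 to 14.7) |
| 20% | 5% | 20.4% (18.0 to 22.9) | 22.0% (19.6 to 24.6) | 23.2% (20.7 to 25.8) |
| 20% | 10% | 20.8% (18.5 to 23.3) | 24.0% (21.5 to 26.6) | 26.4% (23.8 to 29.1) |

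The added term s × q × (1 − b) is never negative, so under this model the bias is upward or nil. It is trivial when q is small, for example tongue numbness after an ear operation. It is material for an uncommon symptom that the surgery often causes.

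**4. Cost of splitting.** Suppose s = 10% at n = 1100, giving 110 and 990 patients. At a 10% rate, the exact interval is 8.3% to 11.9% for 110/1100 and 8.2% to 12.0% for 99/990. The larger group loses almost nothing. The smaller group is imprecise: 55/110 gives 40.3% to 59.7%.

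**The case against.** The strongest reply is that attribution is already provided for. Objective 6 is worded in terms of attribution. A symptom reported at interview can meet the section 9.1.1 definition of an adverse event, and section 9.2 then calls for a medically qualified judgement of relatedness. On this view only a linking sentence is missing. The reply shows that attribution is intended. It does not close the gap, because nothing says the judgement decides which symptoms count for objective 6. Under section 9.1.2 a reasonable possibility is enough, and a sore throat after oral surgery with the device in place would usually meet that test.

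A second reply is that section 10 does not forbid a breakdown by operation, and the operation is recorded. That stands: the information is not lost, and it would be an inference to say that only pooled rates are planned. But a split chosen after the symptom data have been seen is weaker than one fixed in advance.

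A third reply is that the effect is hypothetical. This also stands in part. A reader might infer that the device's complication rates will be inflated. The documents do not support that, because they give no case mix and the effect is nil if no such operations are enrolled. A reader might also infer that the study's main conclusions are compromised. They are not: section 4 places the primary outcomes at the time of anaesthesia, the interim analysis looks at device failure, and the sample size does not rest on symptoms.

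Finally, the protocol states no plan to compare these symptom rates with those of other devices, so loss of comparability is not a fault in a planned analysis.

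**Conclusion.** The point holds in a limited and conditional form. The plan names airway-attributed post-operative complications as an objective, collects symptoms without cause, admits surgery on the same areas, has no comparator, and sets out no analysis that would separate the two. If such operations are enrolled, the secondary symptom rates can be biased upward as estimates of device effect.

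The size cannot be derived from the documents. On assumed inputs (5% of operations on these areas, surgical symptom probability 0.1 to 0.8), a 5% rate would be observed as 5.5% to 8.8%, and a 20% rate as 20.4% to 23.2%. Nothing beyond the secondary post-operative symptom rates is affected. It is worth correcting before the data are seen because the correction is cheap.

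**What to change.** In sections 10.1 and 10.3, pre-specify that each post-operative symptom rate, with its binomial 95% interval, is reported for all patients and separately for (a) operations on the head, mouth, nose, ear, throat or neck and (b) all other operations. Classify from the recorded operation, by someone without sight of the symptom data. State that the interpretation of objective 6 draws on group (b) alongside the all-patient rate.

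Group (b) should not replace the all-patient rate as the only headline, since that would change the population for the objective and set aside eligible users of the device. Group (b) is also not a pure device effect: symptoms present before surgery and other peri-operative causes remain in it.

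The cost is a sentence or two in the analysis section and a coding step on a variable already collected. Intervals are slightly wider in group (b) and much wider in group (a) if it is small. Eligibility, visits and care are unchanged.
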